In your recruitment plan, how many different populations of prospective subjects do you plan to target? Provide number: 2

Identify the criteria for **inclusion**:

Identify the criteria for **exclusion**:

e.g., a population can be individuals with type 2 diabetes controlled with diet and/or a population of healthy controls. Or a population can be individuals attending an education program, etc.
 
List each different population on a separate row and provide a short descriptive label: (e.g., normal-healthy, diabetics, parents, children, etc.)
 
To add rows use copy & paste
		
Type 2 diabetic subjects	1) FPG< 240 mg/dl 2) Age 18-70 years 3) eGFR>60 ml/min 4) weight stable ($\pm 4\text{Lb}$) in the preceding 3 months 5) Good general health	1) Use of an insulin or SGLT2 inhibitor medications affects glucose tolerance 2) Major organ disease 3) eGFR <60 ml/min 4) type 1 diabetes
Subjects with FPG<126 mg/dl	1) FPG<126 and 2-h PG <200 mg/dl 2) Age 18-70 years 3) eGFR>60 ml/min 4) weight stable ($\pm 4\text{Lb}$) in the preceding 3 months 5) Good general health	1) Use of medications that affect glucose tolerance 2) Major organ disease 3) eGFR <60 ml/min
Sub-Study: Type 2 diabetic	1) current diagnosis of Type 2 Diabetes 2) fasting plasma glucose concentration <300 mg/dl 3) Subjects must be drug naïve or on stable dose of metformin and/or sulfonylurea in the preceding 3 months 4) body weight has been stable (± 3 lbs) over the preceding three months 5) does not participate in an excessively heavy exercise 6) good general health as determined by physical exam, medical history, blood chemistries, CBC, TSH, urinalysis, and EKG	1) eGFR > 60 ml/min 2) hematocrit > 34%, 3) allergy to iodine 4) Major organ disease
Sub-Study: non-diabetic	1) No diagnosis of diabetes (FPG <126 mg/dl) 2) body weight has been stable (± 3 lbs) over the preceding three months 3) does not participate in an excessively heavy exercise 4) good general health as determined by physical exam, medical history, blood chemistries, CBC, TSH, urinalysis, and EKG	1) eGFR > 60 ml/min 2) hematocrit > 34%, 3) allergy to iodine 4) Major organ disease

Item 6

Research Plan / Description of the Research Methods *a. Provide a comprehensive narrative describing the research methods. Provide the plan for data analysis (include as applicable the sample size calculation).*

Step-by-Step Methods: Study Design:

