Follow Up Visits: at weeks 1, 2, 4, 6, 8 and 10 after the start of treatments, subjects will come to the CRC for follow-up visits. At week 4 and 8 visits, medical history and physical exam will be performed. Body weight, blood pressure and pulse will be measured. Blood sample will be drawn for the measurement of fasting plasma glucose, insulin, glucagon, FFA, HbA1c, Pro BNP and ketones. Blood will also be drawn to monitor renal function with ketones, electrolytes, glucosuria, and monitor and mitigate urinary tract infections.

If the treatment period is extended, patients will continue to be followed up every 2-4 weeks and provided with the study medications until the repeat tests are completed. If the circumstances prohibit clinic visits for follow-up, the study team will perform a phone follow-up visit to ensure patient adherence, information collection, and adverse events monitoring.

Sub-Study 1:

36 T2DM patients will participate in this study, The T2DM subjects enrolled in the main study will also be subjects enrolled into the sub-study. Each subject will receive a measurements of hepatic glucose production with stable isotope (6,6,-D2-glucose) plus indirect calorimetry with empagliflozin (n=24) or placebo (n=12) administration. Norepinephrine turnover measurement will be performed at baseline (before the empagliflozin or placebo administration) and 5 hours after the drug administration. On a separate day subjects will return to the CRC and the measurement of hepatic glucose production and NE turnover studies will be repeated with a glucose clamp.

Specific Methods:

Measurement of Hepatic Glucose Production With 6,6,D2-glucose, ³H-NE infusion and Drug Administration:

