In initial studies, we observed that the increase in EGP after empagliflozin administration is influenced by the amount of fluids (saline infused intravenously plus amount of water drank by patient) taken by the patient during the study. Because empagliflozin causes glucosuria, and increase in urinary sodium and fluid excretion, this observation raises the possibility that plasma volume is an important parameter in the action of SGLT2 inhibitors. Further, since decreased plasma volume is strong stimulus of sympathetic activity, the decrease in plasma volume could

provide the link between empagliflozin and sympathetic activation (which is the primary focus of the present study).

To explore possible role of change in plasma volume in the link between empagliflozin administration and increase in EGP, we request to add a pilot study (Sub-study 2) in which the effect of empagliflozin (or placebo) on EGP production is measured with and without replacement of fluids lost in the urine during the study.

Research Design and Methods:

Subjects: Two groups of subjects will participate in this sub-study: (1) 36 T2DM patients, and (2) 18 non-diabetic healthy subjects . T2DM subjects must have fasting plasma glucose concentration <300 mg/dl. There is no limit on the upper level of HbA1c. Subjects must be drug naïve or on stable dose of metformin and/or sulfonylurea in the preceding 3 months. Other than diabetes, subjects must be in good general health as determined by physical exam, medical history, blood chemistries, CBC, TSH, urinalysis, and EKG. Only subjects whose body weight has been stable (\pm 3 lbs) over the preceding three months and who do not participate in an excessively heavy exercise program will be included. Individuals with eGFR < 60 ml/min, hematocrit <34%, and subjects with allergy to iodine will be excluded.

Pregnant women and women planning to become pregnant will be excluded from the study. We will perform a pregnancy test at the time of screening. Women of child bearing age will be requested to use at least one barrier method before being enrolled in the study.

Study Design:

After screening, eligible subjects will receive DEXA scan and 4 measurements of EGP as described below.

Each EGP measurement will be performed on a different day 1-3 weeks apart, after 10-12 hour overnight fast. Subjects will be instructed to ingest a weight maintaining diet containing 45% CHO, 25% fat, and 30% protein throughout the entire study period.

EGP Measurement

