Indocyanine Green (ICG): is approved by the FDA for the measurement of cardiac output and hepatic function. It is cleared from the body by excretion to the biliary system. The only known adverse event is allergic reaction to iodine. Subjects with allergy to iodine will be excluded from the study. Although ICG is rapidly cleared from the body, it is recommended that subjects will not perform radioiodine uptake studies until one week after the use of ICG.

Empagliflozin: approved by the FDA for the treatment of T2DM. All patients in this sub-study have T2DM. The drug increases the risk of genital and urinary infections by ~5%. Rare adverse events (<1%) include volume depletion, decreased blood pressure, ketoacidosis, necrotizing fasciitis, and acute kidney injury. These adverse events were observed with long treatment (6 months) with the drug. However, subjects will receive only two tablets in the present study.

Assessment of adverse events

Definitions of adverse events:

Adverse event - An AE is defined as any untoward medical occurrence in a patient or clinical investigation subject administered a medicinal product and which does not necessarily have to have a causal relationship with this treatment.

An AE can therefore be any unfavorable and unintended sign (including an abnormal laboratory finding), symptom, or disease temporally associated with the use of a medicinal product, whether or not considered related to the medicinal product.

The following should also be recorded as an AE in the CRF and SAE form (if applicable):

- Worsening of the underlying disease or of other pre-existing conditions
- Changes in vital signs, ECG, physical examination and laboratory test results, if they are judged clinically relevant by the investigator

Serious adverse event:

A serious adverse event (SAE) is defined as any AE, which fulfils at least one of the following criteria:

- results in death,
- is life-threatening, which refers to an event in which the patient was at risk of death at the time of the event; it does not refer to an event that hypothetically might have caused death if more severe,
- requires inpatient hospitalization or prolongation of existing hospitalization
- results in persistent or significant disability or incapacity,
- is a congenital anomaly / birth defect,

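### Item 5 excludes sub-study candidates with eGFR above 60 and hematocrit above 34%, the reverse of the Sub-Study 2 text, and does not say which sub-study it governs

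*Combined protocol and SAP*

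**What the plan says.** Eligibility for the sub-studies is stated in two places.

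- **Item 5, sub-study rows.** The exclusion cell is the same in the T2DM row and the non-diabetic row: "1) eGFR > 60 ml/min 2) hematocrit > 34%, 3) allergy to iodine 4) Major organ disease". The inclusion cells of both rows require "good general health as determined by physical exam, medical history, blood chemistries, CBC, TSH, urinalysis, and EKG". The row labels say only that they concern a sub-study and give no number.
- **Item 6, Sub-Study 2, Subjects.** "Individuals with eGFR < 60 ml/min, hematocrit <34%, and subjects with allergy to iodine will be excluded".

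Two other places bear on the reading.

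- **Item 5, main-study rows.** The T2DM row lists as exclusions "2) Major organ disease 3) eGFR <60 ml/min 4) type 1 diabetes". The non-diabetic row also excludes eGFR below 60, and both rows require eGFR above 60 for inclusion. Neither has a hematocrit criterion.
- **Item 6, Sub-Study 1.** "The T2DM subjects enrolled in the main study will also be subjects enrolled into the sub-study".

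For Sub-Study 2, the Subjects paragraph plans "1) 36 T2DM patients, and (2) 18 non-diabetic healthy subjects", while the risk section says "All patients in this sub-study have T2DM".

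**The concern.** The two statements of the Sub-Study 2 exclusions point in opposite directions on renal function and on hematocrit. Both are current, operative text, and neither defers to the other. A screener working from the table and a screener working from the narrative would make opposite decisions on almost every candidate.

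The two criteria matter in this sub-study. Each subject has four measurements with 165 ml of blood drawn at each. Empagliflozin is given at two of them, once with and once without fluid replacement. The Measurement III text cites about 600 ml of extra urine and about 70 meq of sodium chloride lost over 8 hours with this drug class, and plasma volume is the factor under test. Renal function and hematocrit therefore bear both on participant protection and on who can inform the mechanism. The documents do not draw this link themselves; it is my inference from the procedures they describe.

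**Working it through.** The plan gives no figure to reproduce. The check is a comparison of the texts, plus simple counts.

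**Step 1. Thresholds side by side**

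| Source | Excludes on eGFR (ml/min) | Excludes on hematocrit | So admits |
|---|---|---|---|
| Item 5, sub-study T2DM row | > 60 | > 34% | eGFR ≤ 60 and hematocrit ≤ 34% |
| Item 5, sub-study non-diabetic row | > 60 | > 34% | eGFR ≤ 60 and hematocrit ≤ 34% |
| Item 6, Sub-Study 2, Subjects | < 60 | < 34% | eGFR ≥ 60 and hematocrit ≥ 34% |
| Item 5, both main-study rows | < 60 (inclusion requires > 60) | none | eGFR > 60 |

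Two criteria in each of two rows conflict with the Sub-Study 2 paragraph: 2 × 2 = 4 entries, although it is one cell repeated.

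**Step 2. Apply the Sub-Study 2 rules together**

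- eGFR: ≤ 60 and ≥ 60 leaves only 60.
- Hematocrit: ≤ 34% and ≥ 34% leaves only 34%.
- The joint region is the single point (60 ml/min, 34%), so in practice almost nobody qualifies.

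**Step 3. Apply the Item 5 rows alone**

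Only people with eGFR at or below 60 and hematocrit at or below 34% remain. The same rows require good general health judged on chemistries, blood count and urinalysis, and exclude major organ disease. Those items would probably remove most of the people left, so the table also sits badly with itself.

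**Step 4. Could this be something other than a contradiction?**

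- *A fault in reading the PDF:* unlikely. The reversal occurs for two criteria in two rows, while less-than signs elsewhere in the same table are intact (the FPG limits and the main-study eGFR exclusions).
- *A list of requirements placed in the wrong column:* this does not fit. Iodine allergy and major organ disease, in the same numbered list, can only be exclusions.
- *Superseded text:* neither place is an amendment log.

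**Step 5. Which sub-study do the rows govern?**

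The FPG limit of 300 mg/dl, the 3 lb weight limit, the iodine-allergy item and the presence of a non-diabetic group all match Sub-Study 2. Sub-Study 1 is described with T2DM subjects only. The inference to Sub-Study 2 is strong, but the table does not state it. If the T2DM row were also read as covering Sub-Study 1, its 36 subjects, who come from the main study with eGFR above 60 required, would all be excluded: eGFR > 60 and eGFR ≤ 60 have no overlap.

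**Step 6. Size and exposure in Sub-Study 2**

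- Planned subjects: 36 + 18 = 54 by the Subjects paragraph; 36 if all have T2DM, as the risk section says.
- Blood drawn: 4 × 165 ml = 660 ml, which agrees with the plan's own total.
- Time span: "Each EGP measurement will be performed on a different day 1-3 weeks apart". Four measurements have three gaps, so 3 × 1 to 3 × 3 = 3 to 9 weeks.

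**The case against.** The strongest reply accepts the conflict and disputes its weight.

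- **The intent is easy to infer.** The Sub-Study 2 paragraph is a complete eligibility statement, and the table read literally would nearly empty the population. An error that obvious would probably be caught at screening rather than quietly admit people at risk. This is fair, and it lowers the chance of harm. It does not settle which of two current texts binds the site.
- **The main-study rows govern a different study.** They also differ from the sub-study rows on FPG (240 against 300 mg/dl) and weight stability (4 against 3 lb) without anyone calling that a contradiction. This stands in part. The main-study eGFR lines run opposite to the sub-study rows and are evidence of direction, but they are not a second rule for Sub-Study 2. The core conflict is between the sub-study rows and the Sub-Study 2 paragraph.
- **The missing label is minor.** The content identifies Sub-Study 2, and the Sub-Study 1 consequence rests on a less likely reading. I agree, and treat that consequence only as conditional.
- **The stakes are modest.** This is a pilot sub-study at one site, no sample size or power figure depends on the point, and 54 or 36 is planned enrolment, not people shown to be affected. All of that is correct. It limits the size of the problem but does not remove the conflict.

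**Conclusion.** The concern holds. Both sub-study rows of Item 5 reverse the eGFR and hematocrit exclusions given in the Sub-Study 2 Subjects paragraph, and the two rules are compatible only at exactly 60 ml/min and 34%. The eGFR direction also runs against both main-study rows. The rows do not name the sub-study they cover.

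The conclusion assumes that the inequality signs were read correctly, which the repeated pattern supports, and that the rows describe Sub-Study 2, which their content supports. It does not depend on any view of which threshold is clinically right. It is a drafting contradiction in binding eligibility text, with no effect on the planned analysis or power. It must be corrected because following the table as written would exclude nearly everyone that the Sub-Study 2 paragraph would admit, and because two incompatible rules should not both be in force.

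**What to change.** - Reconcile the eGFR and hematocrit exclusions in both Item 5 sub-study rows with the Sub-Study 2 Subjects paragraph, and check the eGFR direction against the main-study rows. The investigators should confirm the intended criteria, and the document should then state them once, identically, in both places.
- Add to each row label the sub-study it governs. If Sub-Study 1 is meant to have its own criteria, or to inherit those of the main study, say so.
- Check whether any screening form was built from the Item 5 wording and whether any subject was screened against it. Document the result.

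The cost is a correction to two table rows, a label, and a short check of screening records. No analysis or sample size needs to be redone.

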Measurement I. Subjects will ingest placebo at time zero, and blood and urine samples will be collected as described above. The retrograde line will be kept patent by infusing 0.5 N saline at 2 ml per hour using high precision infusion pumps (2ml/hour x 7 hours = 14 ml total over 7 hours).

Measurement II. Subjects will ingest empagliflozin (25 mg) at time zero, and blood and urine samples will be collected as described above. Each intravenous line will be kept patent as described in Measurement I. Using this protocol we previously have shown that SGLT2i (dapagliflozin, empagliflozin, and canagliflozin) stimulate endogenous glucose production (EGP) compared to placebo and increase plasma ketone concentration by 0.3-0.6 mmol/L, in association with a 4-7 μ U/ml decrement in plasma insulin concentration that was paralleled by a similar decrease in plasma C-peptide concentration and increase in plasma glucagon concentration (3).

Measurement III. Subjects will ingest empagliflozin (25 mg) at time zero and blood and urine samples will be collected as described above. At time zero, an intravenous infusion of saline will be started to replace the amount of fluid and electrolytes excreted in the urine during the EGP measurement without volume replacement. Approximately 70 meq of Na⁺ and 70 meq of Cl⁻ are excreted in the urine by SGLT2i treatment within 6 hours. Thus, 2.2 ml/min (of half normal saline), or 1.1 ml/min of normal saline (0.9%) will be infused until the study end at 420 minute. In previous studies with empagliflozin, as well as with dapagliflozin and canagliflozin (3,5), we demonstrated that 8-hour urine volume and 8-hour urine sodium chloride excretion increased by ~600 ml and ~70 meq, respectively. Thus, administration of 462 ml (or 924 ml if normal saline is infused) of fluid and 70 meq of Na⁺-Cl⁻ over a 7-hour period should be more than sufficient to prevent any decrease in plasma (represents 5% of body weight), and extracellular (represents 20% of body weight) fluid volume. The measurement of plasma volume with ICG will document the absence of any change (decrease) in fluid space. In addition we will measure NT proBNP throughout the study.

Measurement IV: This measurement will be performed similar to Measurement III with one difference. At time zero, subjects will ingest placebo instead of empagliflozin.

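### Sub-Study 2, Measurement III: the total infusion volumes contradict the stated infusion rates and the stated 70 meq, and no basis is given for using one of the two permitted fluids rather than the other

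*Combined protocol and SAP*

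**What the plan says.** All references are to Item 6, Sub-Study 2.

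- **Rationale.** The sub-study was added because the rise in endogenous glucose production (EGP) after empagliflozin "is influenced by the amount of fluids (saline infused intravenously plus amount of water drank by patient) taken by the patient during the study".
- **Aim of the infusion (Measurement III).** Saline is started at time zero "to replace the amount of fluid and electrolytes excreted in the urine during the EGP measurement without volume replacement".
- **Rates.** "Thus, 2.2 ml/min (of half normal saline), or 1.1 ml/min of normal saline (0.9%) will be infused until the study end at 420 minute".
- **Loss to be replaced.** From earlier studies, "8-hour urine volume and 8-hour urine sodium chloride excretion increased by ~600 ml and ~70 meq, respectively".
- **Totals.** "Thus, administration of 462 ml (or 924 ml if normal saline is infused) of fluid and 70 meq of" sodium chloride over seven hours, which the plan considers ample to prevent any fall in plasma or extracellular volume.
- **Measurement IV.** "This measurement will be performed similar to Measurement III with one difference", namely placebo in place of empagliflozin.
- **Analysis.** The difference between Measurements II and III is read as the contribution of intravascular volume depletion to the EGP response, and is compared with the difference between Measurements I and IV.

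**The concern.** The sentence with the rates and the sentence with the totals describe the same infusion in the same paragraph, but they attach the two volumes to opposite fluids. A reader who works from the totals would plan a different sodium load from one who works from the rates.

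A second, smaller matter lies behind this. The two fluids are joined only by an 'or'. At the stated rates they deliver the same sodium in volumes that differ twofold. The stated aim covers fluid as well as electrolytes, and the rationale names the amount of fluid, infused and drunk, as what influences the EGP response. The sub-study text does not say how the fluid is chosen across subjects, nor that water intake is fixed or recorded.

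The infusion is the experimental manipulation of this sub-study. If its content is ambiguous or varies between subjects, the contrast between Measurements II and III no longer refers to one defined degree of replacement.

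**Working it through.** **Inputs from Measurement III.** Rates of 2.2 ml/min (half normal) and 1.1 ml/min (normal, 0.9%); start at time zero, end at 420 min; stated totals of 462 ml, or 924 ml if normal saline; stated sodium chloride load of 70 meq; cited extra urine volume of about 600 ml over 8 hours.

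**Input not printed in the plan.** Sodium concentration, by chemical conversion: 0.9% sodium chloride is 9 g/L, and 9 / 58.44 = 0.154 mol/L, so normal saline holds 154 meq/L and half normal 77 meq/L.

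**Step 1: totals from the stated rates** (volume = rate × time; sodium = volume × concentration).

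| Fluid | Volume | Sodium |
|---|---|---|
| Half normal | 2.2 × 420 = 924 ml | 0.924 × 77 = 71.1 meq |
| Normal | 1.1 × 420 = 462 ml | 0.462 × 154 = 71.1 meq |

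Both printed volumes are reproduced, and both options agree with the stated 70 meq. The fluid labels are the reverse of those in the totals sentence.

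**Step 2: totals as labelled.** The sentence names normal saline for 924 ml, so 462 ml belongs to half normal by elimination.

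| Fluid | Volume as labelled | Sodium | Implied rate |
|---|---|---|---|
| Half normal | 462 ml | 0.462 × 77 = 35.6 meq | 462 / 420 = 1.1 ml/min |
| Normal | 924 ml | 0.924 × 154 = 142.3 meq | 924 / 420 = 2.2 ml/min |

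These loads are about half and about twice the 70 meq in the same sentence, and the implied rates are the stated rates exchanged. Working back from 70 meq gives the same answer: 70 / 0.924 = 75.8 meq/L, close to half normal, and 70 / 0.462 = 151.5 meq/L, close to normal.

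**Step 3: could another duration explain the labels?** 360 min gives 792 ml half normal and 396 ml normal; 480 min gives 1056 ml and 528 ml. At the stated rates the half normal volume is twice the normal volume at every duration, so no choice of time reverses the pairing.

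**Step 4: the two options compared.** They differ by 924 − 462 = 462 ml at equal sodium. Against the cited 600 ml they are 462 / 600 = 77% and 924 / 600 = 154%. They match each other on sodium but cannot both match the same fluid loss.

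**The case against.** The strongest reply is that the rate sentence is the working instruction. It names fluid, rate and end time and agrees with 70 meq, whereas the totals appear afterwards in a justification. Staff who follow the rates would give about 71 meq with either fluid. This stands, and it limits the consequence: the 36 and 142 meq loads arise only if someone works from the totals. It does not remove the contradiction, and agreement between the rates and the 70 meq does not by itself settle which figures the investigator intended.

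On the choice of fluid, several points also stand. The absence of a rule is largely missing detail, and the 'or' may simply precede one choice for everyone. Measurement IV already mirrors Measurement III, so the I–IV difference serves as a control for the infusion. Plasma volume by indocyanine green (ICG), NT-proBNP, and urine volume and sodium are all measured and would help show what the replacement achieved. The sub-study calls itself a pilot. What remains is that these measurements describe the result and do not standardise what is given.

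A reader might go further in four ways that the documents do not support:

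- *That subjects would receive twice or half the intended sodium.* Nothing shows that the totals would be followed in preference to the rates.
- *That water intake goes unrecorded.* The text does not say that it is recorded, but the scheme figure and case report forms are not available to check.
- *That 462 ml would fail to maintain volume.* The 600 ml is an 8-hour figure set against a 7-hour infusion, sodium matches the cited loss, and water drunk is not specified.
- *That the 70 meq is inconsistent because it is said elsewhere to be lost within 6 hours and here over 8.* Both can hold if most of the loss is early.

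**Conclusion.** The contradiction holds. Measurement III, and through it Measurement IV, gives rates that yield 924 ml of half normal or 462 ml of normal saline (about 71 meq each), and then totals that as labelled imply about 36 or 142 meq against the 70 meq beside them. This rests on the plan's own rates and end time, on the standard concentration of 0.9% saline, and on reading the unlabelled 462 ml as half normal.

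The absence of a stated basis for choosing between the two options is a lesser point. It matters because they differ by 462 ml in a sub-study about volume. A mix across subjects would make the replacement heterogeneous and the II–III contrast harder to interpret. It would be too strong to infer that the contrast is biased: no direction or size of effect on EGP can be derived from the documents, and nothing shows that fluids would in fact be mixed.

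The point should be fixed because the figures define the intervention and the correction is simple. It does not call the design of the sub-study into question.

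**What to change.** The investigator should:

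1. Reconcile fluid, rate, total volume and sodium load within Measurement III. Which figures are right is the investigator's decision.
2. State that one infusion is used consistently, including in a subject's Measurements III and IV.
3. Limit the statement that the infusion is ample to what the reconciled figures support.
4. Record fluid type, infused volume and water drunk in all four measurements, beside the urine volume already collected.
5. Report net fluid balance and the change in ICG plasma volume beside the II–III and I–IV contrasts.

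The cost is a wording correction in one section, a few recorded items and one small table. No additional subjects, visits or procedures are needed.

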Data Analysis and Statistical Methods. Under steady-state postabsorptive conditions, the basal rate of endogenous glucose appearance ($R_a = bEGP$) equals $3\text{-}3\text{H}\text{-glucsoe}$ infusion rate divided by steady state plasma tritiated glucose specific activity. After drug administration, non-steady conditions for $3\text{-}3\text{H}\text{-glucose}$ specific activity prevail and the rate of whole body of glucose appearance (R_a) is calculated from the Steele equation. The difference in EGP during the last half hour of the study (390 to 420 minutes) between subjects receiving empagliflozin (Measurement II) vs placebo (Measurement I) represents the increase in EGP caused by empagliflozin. The difference in EGP between subjects receiving empagliflozin without volume repletion (Measurement II) versus with volume repletion (Measurement III) represents the role of intravascular volume depletion in the stimulation of EGP. The difference in the change in EPG between Measurement II and Measurement III will be compared to the difference between Measurement I and Measurement IV will be compared with ANOVA. Post hoc testing will be performed with Bonferroni correction for multiple comparisons.

The same statistical/analytical approach will be employed for the measurement of plasma FFA, and beta-OH-butyrate concentrations.

Sample Size Calculation. In previous studies, we demonstrated that the mean difference in EGP during the last hour of EGP measurement in empagliflozin-treated (Measurement II) and placebo-treated (Measurement I) subjects was $0.70 \pm 0.34 \text{ mg/kg}\cdot\text{min}$ (mean \pm SD) (3). To detect a 50% decrease in this difference at alpha <0.05 during the volume repletion study (Measurement III) with 90% power and alpha = 0.0125 ($=0.05/4$), we computed that 32 subjects are required. Therefore, to ensure 32 completers, we have set the sample size at 36.

Risks in Sub-Study 2:

Blood loss: blood loss in sub-study 2 will be 165 ml at each EGP measurement. Thus, the total blood loss will be 660 ml

Radiation: total amount of radiation in sub-study 2 will be 59.6 mrem (13.4 at each EGP measurement and 6 mrem at DEXA scan)

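### Sub-study 2 reads Measurement II versus III alone as the role of volume depletion, although that difference contains any effect of saline itself, and does not say whether it or the ANOVA contrast governs

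*Combined protocol and SAP*

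**What the plan says.** The text is in Item 6, Sub-Study 2. After screening, "eligible subjects will receive DEXA scan and 4 measurements of EGP", so each subject contributes all four conditions. There are two groups: "1) 36 T2DM patients, and (2) 18 non-diabetic healthy subjects".

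| | No saline replacement | Saline replacement |
|---|---|---|
| Placebo | I | IV |
| Empagliflozin | II | III |

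In Measurement III, "an intravenous infusion of saline will be started to replace the amount of fluid and electrolytes excreted in the urine". Measurement IV is the same with one change: "At time zero, subjects will ingest placebo instead of empagliflozin".

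The paragraph on data analysis and statistical methods then makes three statements in a row:

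- II versus I is the rise in EGP caused by empagliflozin.
- Empagliflozin without repletion (II) "versus with volume repletion (Measurement III) represents the role of intravascular volume depletion in the stimulation of EGP".
- The II-to-III difference "will be compared to the difference between Measurement I and Measurement IV will be compared with ANOVA".

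Bonferroni post hoc tests follow, but the comparisons are not listed. The approach carries over to other outcomes: "The same statistical/analytical approach will be employed for the measurement of plasma FFA, and beta-OH-butyrate concentrations". No contrast is named as primary.

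**The concern.** The second and third statements describe different quantities. II−III is the effect of saline in subjects who took the drug. It equals the volume-mediated part of the drug effect only if saline does nothing to EGP in subjects who did not take it. The third statement allows for this by setting II−III against I−IV; the second does not.

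The worry follows from the sub-study's own rationale, which treats a fall in plasma volume as a strong sympathetic stimulus and a possible link to EGP. Placebo subjects are also fasted overnight and give 165 ml of blood per session, so saline could plausibly change their EGP too.

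At stake is the sub-study's central conclusion. The same data could show a significant II versus III and a null difference-in-differences. The plan does not say which would be reported as the role of volume depletion.

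**Working it through.** **Inputs.** From the sub-study's sample size paragraph: II−I is 0.70 with SD 0.34 mg/kg·min; the target is a 50% decrease, 0.5 × 0.70 = 0.35; power 90%; alpha 0.05/4 = 0.0125; 32 completers from 36 enrolled. Sidedness is not stated, and I assume two-sided. The saline effects are my assumptions.

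**1. What each contrast estimates.** Let S = I−IV be the effect of saline without the drug, and V the part of the drug effect that repletion removes beyond S. Then

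- II−III = V + S
- (II−III) − (I−IV) = (V + S) − S = V

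The two agree only if S = 0. The second is identical to (II−I) − (III−IV).

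**2. The plan's figure of 32.** I used a one-sample t test on within-subject contrasts, with noncentral-t power, difference 0.35 and two-sided 0.0125.

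| Reading of 0.34 | II versus III: SD, n for 90% | (II−III)−(I−IV): SD, n for 90% |
|---|---|---|
| SD of each difference; differences uncorrelated | 0.34, n = 17 | 0.34√2 = 0.481, n = 31 |
| Single-session SD; sessions uncorrelated | 0.34√2 = 0.481, n = 31 | 0.34√4 = 0.68, n = 58 |

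So 31, close to the stated 32, arises for either contrast, depending on what 0.34 is.

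**3. False attribution by II versus III when V = 0.** With n = 32 the critical value is t = 2.65 on 31 df. The noncentrality is S/(SD/√32), where SD/√32 is 0.0601 for SD 0.34 and 0.0850 for SD 0.481. For example, S = 0.10 gives 0.10/0.0601 = 1.66 and rejection probability 18%.

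| Assumed S (mg/kg·min) | Share of 0.70 | SD 0.34 | SD 0.481 |
|---|---|---|---|
| 0.05 | 7% | 4% | 3% |
| 0.10 | 14% | 18% | 8% |
| 0.15 | 21% | 45% | 21% |
| 0.20 | 29% | 75% | 40% |

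The test of (II−III)−(I−IV) rejects 1.25% of the time throughout.

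**4. Bias in the estimate when V = 0.35.** S = +0.10 makes II−III 0.45, or 64% of 0.70. S = −0.10 makes it 0.25, or 36%. A saline effect can inflate or hide mediation.

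**5. Power of (II−III)−(I−IV) at n = 32, difference 0.35.**

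| Assumption | Contrast SD | Power |
|---|---|---|
| 0.34 is the SD of each difference; correlation 0 | 0.481 | 92% |
| Same, correlation −0.25 | 0.538 | 84% |
| 0.34 is a single-session SD; correlation 0 | 0.68 | 61% |

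**6. Where the difference-in-differences itself misleads.** Suppose EGP falls linearly with plasma volume, the whole 0.70 is volume-mediated, and saline raises volume in both conditions by exactly what the drug removes. With I = x, II = x + 0.70, III = x and IV = x − 0.70. Then II−III = 0.70, correctly showing full mediation, while (II−III)−(I−IV) = 0.70 − 0.70 = 0.

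**The case against.** The strongest reply is that the plan already contains the remedy. The only comparison tied to a named test is II−III against I−IV. The sentence about II versus III can be read as defining a component, parallel to the one before it about II versus I. The sub-study is also described as a pilot meant to explore. This stands in part: a reader might infer that the plan tests mediation by II versus III and ignores the saline control, and the text does not support that. But the sentence that assigns the mechanistic meaning assigns it to II versus III, and the ANOVA sentence does not withdraw it.

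The second reply is that I−IV need not be a nuisance. Placebo subjects receive the infusion without the drug-induced loss, so their saline effect may itself come from volume expansion. Step 6 shows that full mediation can then give a null difference-in-differences. This stands, and it rules out treating that contrast as the sole valid measure of mediation. The planned ICG plasma volumes, before dosing and at 380 minutes, bear on whether expansion occurred.

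The third reply is that 0.05 to 0.20 mg/kg·min are invented saline effects, and the larger SD roughly halves the upper probabilities. That is correct; they show sensitivity and do not predict what will happen.

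**Conclusion.** The point holds. II−III is given a meaning it carries only if saline has no effect on EGP without the drug, and the plan does not say which of its two contrasts governs. If there is no mediation, II versus III would be significant 4 to 75% of the time over the assumed saline effects at SD 0.34, or 3 to 40% at SD 0.481 (32 completers, two-sided 0.0125).

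Two further readings are tempting and are not supported. A reader might infer that 32 was derived for the difference-in-differences; step 2 shows that it does not settle this, and the sample size text names Measurement III but not IV. A reader might also infer a serious multiplicity problem from the repeat on FFA and beta-OH-butyrate. That depends on testing each outcome at 0.05. At the 0.0125 used for the sample size, three independent tests give 1 − 0.9875³ = 3.7%, and the documents give no reason to make those outcomes conditional on EGP.

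**What to change.** Replace the sentence that equates II versus III with the role of volume depletion by:

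> The primary test is the within-subject contrast (II−I) minus (III−IV) for EGP at 390–420 minutes. II versus III is supportive, is not read alone as the role of volume depletion, and is reported with I versus IV and the ICG plasma-volume changes in III and IV.

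Add the assumption:

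> A null contrast excludes mediation only if saline did not itself lower EGP by expanding volume on placebo; the ICG data will be used to help judge this.

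The sample size paragraph should also say whether 0.34 is the SD of a within-subject difference or of a single session, because power at 32 ranges from 92% to 61% across the readings in step 5.

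The cost is wording, since all four measurements and the ICG volumes are already planned. The downside is a larger standard error than for II versus III alone: 0.0850 against 0.0601 if 0.34 is the SD of each difference and the differences are uncorrelated.
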